**Calculations;**

- i. HOMA-IR : HOMA- IR index, a commonly used marker of IR, will be calculated using the formula:  $\text{HOMA-IR} = \frac{\text{fasting glucose levels [mmol/L]} \times \text{fasting insulin levels } [\mu\text{U/mL}]}{22.5}$  (34).
- ii. Free Androgen Index will be derived from TT and SHBG, normally measured in nanomoles per liter.  $\text{FAI} = 100 (\text{TT} / \text{SHBG})$

**Outcome : Follow- up visits at 12 weeks (Study Mid Pont):** At 12 weeks follow up, compliance to supplementation and occurrence of any adverse effect will be assessed by research team allocated members in the respective clinics. Moreover, drug for 12 weeks (as per group allocation) will be dispensed and any other queries of participants will be responded. Fasting blood sample (10 ml) will be collected for estimation of SHBG, TT, Human Insulin, Glucose, serum calcium and phosphorous and TAC in both groups and VD and serum albumin estimation in Group A. At this point of time, **treatment protocol of both groups will be changed** (Table 2).

1. **Follow- up visits at 24 weeks (study End Point):** After completion of 24 weeks study exposure, subjects will be informed about completion of study. Blood samples in fasting state will be collected for repeat analysis in Multi Disciplinary Lab (MDL) for all the biochemical parameters (FAI, HOMA IR and TAC) and VD and serum albumin estimation in Group B. Figure 6: Complete cycle of each patient in control and intervention group for a period of 24 weeks

**Biohazardous Samples:** According to the WHO the serum samples have low viral concentration. However, the centrifugation is a risk for aerosol generation and COVID exposure. To minimize the risk, we will ; Train the research staff about the Basics of Biosafety, Biosecurity & Bio risk Management approach for collection & processing of samples. All samples will be treated as potentially infectious, use of proper PPE will be mandatory while handling samples. After centrifugation, staff will wait for 10 minutes before opening the centrifuge. In case of Breakage the already defined laboratory protocols (available in safety manual) will be followed. For liquid waste disposal, will use 5% Hypochlorite.

**Potential Risks:** The potential risks likely to occur in this study are; Loss of patients during movement in respective clinics (Lost to follow up) Noncompliance of subjects, Biosafety Issues, At the time of collection of samples, unexpected delays in the processing of samples; during bench work in MDL lab and Drug Overdose

**Risk management Plan for Potential Risks:**

- i. **Movement of Subjects:** We have hired 2 Research Assistants (RA) who will be in connection with the PI and Co-PIs (Gynecologists and Endocrinologists) to guide the included patients from clinics to CTU, blood collection point and follow up sessions at 12 and 24 weeks.
- ii. **Compliance:** PI students and RA will be in communication with the subjects on emails, phone calls and WhatsApp group, will send them reminders to take their medicine, come for follow up visits and inform if any side effects occur

- iii. Biosafety Issues: Collection of Samples: For the entire research procedure the risks of having blood drawn include temporary pain from the needle stick, bruising, and rarely, infection. Any gross reaction will be reported and informed to the concerned investigator. Unexpected load: Due to pandemic situation, there is an unexpected load on the centrifuge machine in MDL. We have therefore requested our mentor [name]; Head of Chemical Pathology and Laboratory Medicine to allow centrifuge of our samples in the clinical lab of AKUH (if required). Bench work in MDL lab as per AKU COVID-19 **Safety Rules:** The research team will follow all the standard revised operating procedures (SOPs) required for biosafety of lab staff during the pandemic in their BSL2 facility. They include; judicious cleaning of labs, minimal 6 feet distance, cleaning of bench with 70% Isopropyl alcohol or 80% ethanol and follow all the other SOPs that are already implemented in the research areas from before the Covid-19 pandemic.
- iv. Drug Safety: The vitamin doses that are planned for use in this study are based upon scientific evidence and recommendations from international societies and are unlikely to cause hypervitaminosis D. However, **if Hypervitaminosis D** occur in a rare situation, it can lead to **hypercalcemia** which can manifest as polyuria, polydipsia, nausea, vomiting, or constipation, muscle weakness, bone pain, weight loss or poor appetite, confusion or disorientation. We will warn all our subjects to inform us in case if any of these symptoms appear and RA will be in touch with them. We will stop the treatment and report to the respective consultant. We will also assess VD status along with calcium and albumin levels after they have received VD and calcium supplementation. All study related adverse effects will be managed and reported to the ERC, Clinical affairs and pharmacy as per institutional policy.

Investigator and study coordinator will follow up any adverse events and serious adverse events.

**Plan of analysis:** Data will be analyzed using STATA version 15. The main analysis for each outcome will be performed at the subject level using the **intention-to-treat (ITT) principle**, meaning that all participants with a recorded outcome will be included in the analysis and will be analyzed according to the treatment group to which they were randomized. Results will be presented as mean and standard error/ median (IQR) for the outcomes. Pretreatment, 12 weeks and 24 weeks post treatment levels of the outcomes will be assessed by repeated measure ANOVA/ Friedman test as appropriate. Categorical variables will be reported as frequency and percentages and will be assessed by chi-square/ fisher exact test. Unadjusted and adjusted beta coefficient with 95% CI will be reported by using Generalized estimating equation (GEE) to determine the association of various independent factors with the outcomes. We will adjust for the independent variables and determine the association of factors causing a greater decline in outcomes by multivariable GEE. Plausible interactions and confounders will also be assessed. A p value of  $< 0.05$  will be considered as significant throughout the study

**Ethical Considerations:** In this research, we will adhere to ethical principles outlined in the Helsinki Declaration for medical research involving human subjects. We will seek approval from the Aga Khan Ethical Review Committee. The participants will be informed about the study's purpose and the possibility of being part of the intervention group based on computer randomization. We will obtain verbal and written consent from eligible participant. To ensure confidentiality, the entire process from participant enrollment to testing and outcome assessment will be handled discreetly. Consent forms and completed questionnaires will be assigned unique codes and securely stored in locked cabinets accessible only to the Principal Investigator. Participant identifiers will be removed, and only codes will be used in subsequent steps. Serum samples will be collected and coded without mentioning names. These samples will be processed at MDL-AKU and disposed of following AKU clinical lab's institutional policies for biological material disposal, which involves sealing them in red bags and incineration. Hard copies questionnaires will be stored and archived for a minimum of 7 years in line with AKU policy. Afterward, information will be deleted from computers, and the forms and questionnaires will be securely shredded. Results and data will be appropriately coded, decoded, and documented.

**Strength & Limitations:** The delayed-start design has **some methodological issues** in comparison with standard parallel-group study design of RCT. Nonetheless the effects of VD develop over time and we do not want to deprive VD deficient PCOS from VD supplementation in both groups, therefore we have selected this study design; **all subjects will be given same dose of VD either before or after standard PCOS care.** To the best of our knowledge this is the **first clinical trial** which will confirm not only the

impact of VD but also **predict the time of its administration**. Novelty of the study is that in addition to the routine parameters of IR and hyperandrogenism, this study will also estimate and document the **improvement in OS** as a result of the replacement therapy.

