## Methodology

**Study Design:** This will be a randomized open label, delayed-start design trial conducted at Aga Khan University at Departments of: Biological & Biomedical Sciences, Pathology and Laboratory Medicine, Medicine (Endocrinology) and Family Medicine for a period of 2 years following approval from Clinical Trials Unit and Ethical Review Committee of Aga Khan University

**Sample Size calculation;** The sample size was calculated by PASS 11 software. In an equivalence test of means using two one-sided tests on data from two-periods, the minimum sample size that we will require is 142, 71 in each group with an inflation of 20% for loss to follow-up to achieve 80% power at a 5% significance level when the true difference between the means is 0.4, the standard deviation of the paired differences is 2.60.

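### The set labelled intention-to-treat is an available-case set, and the three-visit tests named beside it exclude women whom that definition includes

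*Protocol*

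**What the plan says.** The Plan of analysis applies the intention-to-treat principle to the main analysis of each outcome and explains it in two parts: "all participants with a recorded outcome will be included in the analysis", and these participants "will be analyzed according to the treatment group to which they were randomized".

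The same paragraph then names the methods. "Pretreatment, 12 weeks and 24 weeks post treatment levels of the outcomes will be assessed" by repeated-measures ANOVA or the Friedman test, as appropriate. GEE is named for unadjusted and adjusted coefficients with 95% confidence intervals. The paragraph does not say which of these is the main analysis.

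Three other places bear on how much this matters:

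- Methodology, Study Design: "This will be a randomized open label, delayed-start design trial".
- Methodology, Sample Size calculation: the minimum is "142, 71 in each group with an inflation of 20% for loss to follow-up".
- Potential Risks: loss to follow-up and noncompliance are both listed as likely.

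Under the treatment table, for the first 12 weeks Group A receives one vitamin D injection with daily calcium, and Group B receives Glucophage XR and Progeffik. Both regimens change after the week-12 visit.

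**The concern.** Intention-to-treat has two elements: everyone randomised is in the analysis set, and each is analysed in the assigned arm. The protocol keeps the second and replaces the first with having a recorded outcome. A result from that set would be reported as intention-to-treat when it is available-case.

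The definition and the tests also disagree. A woman measured at week 12 and lost before week 24 has a recorded outcome, so the definition includes her, but a test that needs all three visits excludes her. Her week-12 value is worth keeping, because week 12 is the last visit before both regimens change and so gives the cleanest contrast between the arms.

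Women know their treatment, and the two arms receive different care, so both the amount of loss and the reasons for it could differ by arm. If loss is related to outcome, the contrast among those observed is not the contrast among those randomised.

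**Working it through.** **Step 1. How each rule treats each pattern of follow-up**

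| Values recorded | Protocol's definition | Friedman, classical repeated-measures ANOVA | GEE |
|---|---|---|---|
| 0, 12, 24 weeks | included | included | included |
| 0, 12 weeks only | included | dropped | included |
| 0, 24 weeks only | included | dropped | included |
| 0 weeks only | no follow-up outcome, so outside the set | dropped | no follow-up information |

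Rows two and three show the conflict. GEE resolves it, at the price of a stronger assumption: without weighting it is generally valid only if data are missing completely at random.

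**Step 2. How many women the plan's allowance covers**

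Inputs: total 142 and 20% inflation (Sample Size calculation).

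- If 20% of those enrolled are lost: 142 × 0.20 = 28.4, about 28.
- If the total was reached by multiplying by 1.2: 142 − 142/1.2 = 142 − 118.3 = 23.7, about 24.

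The 142 cannot be reproduced from the stated inputs, because no equivalence margin is given. With an assumed margin of 1.0, two one-sided tests at 5% with 80% power, true difference 0.4 and SD of paired differences 2.60 need 118 in the two-period form, or 59 per group. Then 59 × 1.2 = 70.8, or 71 per group, which favours the second reading. This is not proof: a parallel-group form with an assumed margin of 1.5 gives 142 before any inflation. Nothing below depends on it.

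**Step 3. Size of a possible bias**

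In one arm, let L be the proportion lost and g the mean of the observed minus the mean of the lost. The full mean is (1 − L) × observed + L × lost, so the observed mean differs from it by L × g. For the contrast between arms:

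bias = L_A × g_A − L_B × g_B

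With the same gap in both arms this becomes (L_A − L_B) × g.

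The document gives neither the imbalance in loss nor the gap, so both are assumed. The gap is expressed in units of the planning SD, 2.60.

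| Imbalance in loss | Gap | Bias |
|---|---|---|
| 0 | any, same in both arms | 0 |
| 5 points | 0.25 SD = 0.65 | 0.05 × 0.65 = 0.03 |
| 10 points | 0.5 SD = 1.30 | 0.10 × 1.30 = 0.13 |
| 15 points | 0.5 SD = 1.30 | 0.15 × 1.30 = 0.20 |

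Equal loss is no guarantee of safety. With 20% lost in each arm and gaps of 0.25 SD in opposite directions, the bias is 0.20 × 0.65 + 0.20 × 0.65 = 0.26. The table illustrates the mechanism and does not bound it.

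**The case against.** The strongest reply is that GEE, named in the same paragraph, produces the planned estimates and uses every available visit, and that a long-format ANOVA fit can also keep partial records. This stands. A reader might infer that week-12 values are discarded throughout the plan. The document does not support that: deletion is certain for Friedman, depends on implementation for ANOVA, and does not apply to GEE. What remains is the mismatch with the tests named for the three-visit comparison, and the assumption GEE makes about missing data.

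Other stronger readings also go too far:

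- *The comparison no longer rests on the randomised groups.* Assignment as randomised is stated. The shortfall is the exclusion of women without outcomes.
- *The result will be biased.* The protocol holds no evidence of unequal loss, and it describes reminders and research assistants to support attendance. Bias is a risk, and zero is a possible value.
- *Up to 28 women will be excluded.* The figure is one reading of a planning allowance and not a ceiling.
- *The bias is a set fraction of the planned effect.* The 0.4 is the true difference assumed in an equivalence calculation, not a target effect, and the 2.60 is an SD of paired differences for an outcome that the paragraph does not name. They give a rough scale only.
- *Sampling stops when treatment stops.* No passage says so.
- *The protocol lacks an imputation plan.* That may sit in a statistical analysis plan that is not shown.

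It is also fair to say that a mixed model learns almost nothing about the arm contrast from a woman with a baseline value only. The gain comes from women with partial follow-up and from the weaker missing-data assumption.

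**Conclusion.** The point holds in this form. The protocol itself fixes an available-case set under the intention-to-treat label, and pairs it with tests that, in the case of Friedman and classical repeated-measures ANOVA, drop women whom the definition includes. Both follow from the text and need no assumption.

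The consequence for the result is a plausible risk of unknown size. Loss of about 24 to 28 of 142 is allowed for, and the open-label arms differ visibly for 12 weeks. Under the assumed imbalances and a common gap, bias runs from 0 to about 0.2 where the SD is 2.60. It can be larger if the reasons for loss differ by arm. The planning calculation is an equivalence test, so a shift in either direction could matter. This is worth correcting in the protocol, but it does not by itself invalidate the trial.

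**What to change.** 1. Define the intention-to-treat set as all randomised women in their assigned arm.
2. For each continuous outcome measured in both arms at all three visits (such as HOMA-IR, FAI and TAC), make the main analysis a likelihood-based linear mixed model with arm, visit and arm-by-visit. Use every available value at 0, 12 and 24 weeks, and transform skewed outcomes. This replaces repeated-measures ANOVA and Friedman. It does not suit vitamin D level, whose follow-up measurement is scheduled in Group A only at week 12 and in Group B only at week 24.
3. Call any analysis limited to women with recorded outcomes available-case.
4. Report loss by arm.

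The cost is protocol wording and slightly more work in Stata, the package already named. The model assumes data missing at random, so it does not remove bias from loss that depends on unobserved values. A sensitivity analysis for that case would be useful support, but its absence here is not part of the error.

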## Cover Letter

### Title:

## Efficacy of Vitamin D Supplementation in Females with Polycystic Ovary Syndrome: A Randomized Open-Label Delayed-Start Design

Clinical Trial Unit,

I am writing to submit my study, titled "Efficacy of Vitamin D Supplementation in Females with Polycystic Ovary Syndrome: A Randomized Open-Label Delayed-Start Design," for consideration in the Clinical Trial Unit. I am excited to present this research project for potential inclusion in your esteemed program.

Polycystic Ovary Syndrome (PCOS) is a prevalent and complex endocrine disorder that affects many women worldwide. The condition is characterized by a range of symptoms, including irregular menstrual cycles, hyperandrogenism, and polycystic ovarian morphology. There is a growing body of evidence suggesting a link between vitamin D deficiency and PCOS, as vitamin D plays a crucial role in various aspects of reproductive health and endocrine regulation.

Our study aims to investigate the efficacy of vitamin D supplementation as a potential therapeutic intervention for females with PCOS. The randomized open-label delayed-start design allows for a comprehensive examination of the long-term effects of vitamin D supplementation on PCOS symptoms and associated comorbidities. By comparing the outcomes between immediate and delayed-start groups, we hope to gain insights into the optimal timing of vitamin D intervention and its impact on the progression of PCOS.

[figure not shown]
The significance of this study lies not only in its potential to improve the quality of life for individuals with PCOS but also in its contribution to the broader field of reproductive medicine. If our findings support the efficacy of vitamin D supplementation, it could lead to the development of cost-effective and accessible treatments for a condition that affects millions of women worldwide.

I believe that the Clinical Trial Unit is the ideal platform for conducting this research due to its commitment to advancing clinical science and improving patient care. Our study adheres to rigorous ethical and methodological standards, and we are confident that it aligns with the objectives and values of your organization.

I kindly request that you consider our study for inclusion in the Clinical Trial Unit and appreciate the opportunity to discuss this research further. The date of ERC approval is 7th December, 2021

Thank you for your time and consideration.

Best Regards,

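### The Friedman alternative named for the three-visit outcomes has no group factor, so it cannot answer the immediate versus delayed-start question; the between-group conclusion should rest on the GEE already planned

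*Protocol*

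**What the plan says.** The Protocol's Cover Letter says what the trial is to learn from: "By comparing the outcomes between immediate and delayed-start groups". Strength & Limitations adds that the trial will speak to both the effect of vitamin D and when to give it. Both are statements about Group A against Group B.

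The Plan of analysis handles the repeated outcomes in two places:

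- Levels over the visits: "Pretreatment, 12 weeks and 24 weeks post treatment levels of the outcomes will be assessed by repeated measure ANOVA/ Friedman test as appropriate".
- GEE, with unadjusted and adjusted coefficients and 95% confidence intervals, is used "to determine the association of various independent factors with the outcomes" and to "determine the association of factors causing a greater decline in outcomes by multivariable GEE". It adds: "Plausible interactions and confounders will also be assessed".

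The same paragraph sets an intention-to-treat rule, "meaning that all participants with a recorded outcome will be included in the analysis", with patients counted in their randomised arm.

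At the 12-week visit, "treatment protocol of both groups will be changed". Table 2 shows active treatment in both groups in both periods.

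**The concern.** The Plan of analysis names two options for the three-visit outcome levels. Repeated-measures ANOVA can carry a between-patient group factor. Friedman cannot: it asks only whether a patient's values tend to be higher at some visits than at others. If the outcomes prove skewed and Friedman is chosen, the test named for those levels does not address the trial's question. That choice is plausible, because HOMA-IR is a product and FAI a ratio, and such measures are often skewed (an assumption; the Protocol does not discuss their distribution).

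The design makes this matter. Group A starts on vitamin D and calcium, Group B on standard PCOS treatment, and both regimens change at week 12. Change from baseline is to be expected in both arms whether or not the arms differ. A significant visit effect could therefore be read as evidence for vitamin D, or for its timing, when it shows only that treated patients changed.

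There is also a conflict within the paragraph. Friedman needs all three visits from each patient, while the stated rule keeps everyone with a recorded outcome. GEE can follow that rule; Friedman cannot.

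**Working it through.** **1. What Friedman tests.** Rank the k = 3 visits within each of n patients and let R_j be the rank sum at visit j. The statistic is

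Q = [12 / (n·k·(k+1))] · ΣR_j² − 3n(k+1), which for k = 3 is Q = ΣR_j²/n − 12n.

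No term refers to group. Two checks with simulated data, 57 per arm:

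- Adding 10 to every Group B value leaves Q unchanged (0.0526 both times).
- If the arms move in opposite directions by 0.5 at week 12 (between- and within-patient SD 1, assumed), pooled Friedman rejects in 5% of trials. A between-group t-test of the 12-week change rejects in 96%.

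**2. Number of completers.** The Protocol gives no figure for the A–B analysis itself to reproduce. Its only related figures are under Sample Size calculation: 71 per group, including 20% for loss. Then 71/1.2 = 59.2, so 59 per arm; the other reading, 71 × 0.8 = 56.8, gives 57. I use 59.

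**3. Equal change, no A–B difference.** Assumed: normal data, 0.3 SD change at weeks 12 and 24 in both arms, equal correlation between visits, 4,000 simulated trials per setting.

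| Share of trials with p < 0.05 | corr. 0.3 | 0.5 | 0.7 |
|---|---|---|---|
| Pooled Friedman, time only | 67% | 82% | 96% |
| Pooled ANOVA, time only | 82% | 93% | 99% |
| ANOVA, group-by-visit | 4.9% | 4.9% | 4.7% |
| Week-12 A–B, baseline-adjusted | 5.0% | 4.6% | 5.2% |
| Week-24 A–B, baseline-adjusted | 3.8% | 4.9% | 5.3% |

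The first two rows are power for a time effect that is really there; the last three are false-positive rates for the A–B question. At 57 per arm and correlation 0.5, the pooled figures are 79% (Friedman) and 91% (ANOVA). Log-normal data give the same Friedman rates, because taking logs leaves within-patient ranks unchanged.

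**4. A real A–B difference of 0.5 SD at week 12, closed by week 24.**

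| Share of trials detecting it | corr. 0.3 | 0.5 | 0.7 |
|---|---|---|---|
| ANOVA, group-by-visit | 65% | 81% | 96% |
| Week-12 A–B, baseline-adjusted, 59 per arm | 81% | 87% | 97% |
| GEE week-12 A–B, all recorded visits | 86% | 91% | 98% |

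The GEE row assumes 71 randomised per arm and 12 lost at random, 6 of them seen at week 12. Its rejection rate with no A–B difference is 5.3–5.5% at week 12. For a 0.5 SD difference at week 24, the GEE week-24 contrast detects 82%, 89% and 97%.

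**5. Values that Friedman discards.** Lost per arm: 71 − 59 = 12, so 24 in all. If one third to two thirds of them are seen at week 12 (assumed), 8 to 16 recorded week-12 values are dropped: 8/(118 + 8) = 6.3% to 16/(118 + 16) = 11.9% of those recorded.

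**The case against.** The strongest reply is that the Plan of analysis gives Friedman a question that it suits, change over visits, and never calls it the A–B test. GEE is planned whichever option is used. The intention-to-treat sentence has little purpose unless arms are compared, and in a two-arm trial the allocated group is the obvious independent factor. Naming model terms and a primary visit is ordinary SAP content, and the SAP is not shown.

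Much of this stands. A reader might infer that the plan contains no A–B comparison at all. The document does not support that: ANOVA or GEE would supply it once group and group-by-visit are entered, and their absence from the Protocol is not in itself an error.

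A reader might also infer that the arms will be tested separately and the p-values set side by side. In the setting of equal 0.3 SD change, Friedman would be significant in exactly one arm in 40–50% of trials despite no A–B difference. That figure applies only if the tests are run that way, which the plan does not state, so it is no part of the conclusion.

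What the reply does not remove is that the named alternative cannot serve the stated aim and conflicts with the paragraph's own inclusion rule. The GEE is meanwhile described as a search for associated factors, with group not mentioned. An SAP could add terms to a model; it could not give Friedman a group factor.

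**Conclusion.** The point holds in a limited form. Friedman, as the stated alternative for the three-visit levels, is a time-only test and cannot support a conclusion about immediate versus delayed start. A significant change over visits, by Friedman or by a time-only ANOVA, is expected here from treatment in both arms. In the illustration, pooled Friedman is significant in 67–96% of trials with no A–B difference, against about 5% for a baseline-adjusted A–B contrast.

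That Friedman has no group factor follows from its definition. The percentages rest on assumed effect sizes, correlations and completer numbers. The loss of 6–12% of recorded week-12 values rests on an assumed split of dropouts; it is a minor inconsistency, and no bias is claimed from it. The detection rates concern a non-zero difference and say nothing about power for equivalence. The point is worth correcting because the remedy is cheap and uses a method already planned.

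**What to change.** In the Plan of analysis:

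1. Base the between-group conclusion on the planned GEE (or a mixed model) with group, visit, group-by-visit and baseline value, using all recorded visits and patients as randomised. Report A minus B with its confidence interval at weeks 12 and 24. Week 12 compares vitamin D plus calcium with standard PCOS treatment. Week 24 compares early with delayed start; by then Group B has had 24 weeks of standard treatment and Group A 12.
2. For skewed outcomes, replace Friedman with a log transformation or a between-group rank method on baseline-adjusted values.
3. Treat time-only ANOVA or Friedman results as descriptive.
4. Reconcile the contrast with Sample Size calculation, which rests on an equivalence test (two one-sided tests). State whether A minus B is judged against an equivalence margin or as a difference, and at which visit.

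Cost: a few sentences and slightly more modelling, with log-scale results reported as ratios. No new data are needed and no treatment changes. Item 4 needs a decision by the investigators as well as wording.

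### The pre-treatment value is analysed as one of three response levels and is not stated to be a covariate; a baseline-adjusted contrast at each visit would be more precise at no cost (minor recommendation)

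*Protocol*

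**What the plan says.** The Plan of analysis (Protocol) names two analyses of the continuous outcomes.

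- Repeated-measures ANOVA or Friedman test: "Pretreatment, 12 weeks and 24 weeks post treatment levels of the outcomes will be assessed by repeated measure ANOVA/ Friedman test as appropriate". The pre-treatment value stands beside weeks 12 and 24 as a level of the response. The sentence names no group term and no group-by-time term.
- GEE, unadjusted and adjusted: "Generalized estimating equation (GEE) to determine the association of various independent factors with the outcomes", followed by "We will adjust for the independent variables and determine the association of factors causing a greater decline in outcomes by multivariable GEE". The adjustment variables are not listed, and the baseline value of the outcome is not mentioned. Interactions are to be assessed where plausible, but none is named.

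The same section says that participants "will be analyzed according to the treatment group to which they were randomized" and sets a p value below 0.05, without sidedness, which "will be considered as significant throughout the study". On size, the Methodology section states: "the minimum sample size that we will require is 142, 71 in each group with an inflation of 20% for loss to follow-up".

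**The concern.** The arms are randomised 1:1, so any group difference before treatment is chance. A baseline measurement of FAI, HOMA-IR or TAC then has one main use in comparing the arms: to remove between-woman variation from the later values. Entering it as a covariate does this with the weight that the data support. Entering it as a further response level and contrasting later visits with it amounts to subtracting it with a weight of one, which is too much whenever the correlation between visits is below 1.

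Precision is at stake, not validity. Both approaches estimate the same week-12 difference without bias in a randomised trial, but the change-type contrast has a wider confidence interval. The trial has 71 women per arm before losses and has already planned to take the baseline measurements, so the precision is available for nothing.

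**Working it through.** **Inputs from the protocol.** 71 per group with a 20% allowance for loss; 1:1 allocation; significance level 0.05. Taking the allowance as a 20% loss, 71 x 0.8 = 56.8, so n = 57 per arm. The protocol gives no precision or power figure for this analysis, so there is none to reproduce. The stated total of 142 is used only for n.

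**Assumptions, none given in the protocol.** Equal variance at each visit (set to 1) and equal correlation rho between any two visits, with rho 0.3, 0.5 and 0.7; a true week-12 difference of 0.5 SD; two-sided testing; a baseline value that precedes the first dose.

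**Step 1: variance per woman for the week-12 contrast.**
- Change from baseline: 2(1 - rho).
- Baseline as covariate: 1 - rho^2.
- Ratio, adjusted to change: (1 - rho^2) / [2(1 - rho)] = (1 + rho)/2, so the reduction is (1 - rho)/2.

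**Step 2: standard error and power.** SE = sqrt((2/57) x variance). Power is from the noncentral t distribution with 112 df (change) or 111 df (adjusted), noncentrality 0.5/SE.

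| rho | Variance: change | Variance: adjusted | Reduction | SE: change | SE: adjusted | Power: change | Power: adjusted |
|---|---|---|---|---|---|---|---|
| 0.3 | 1.40 | 0.91 | 35% | 0.222 | 0.179 | 61% | 79% |
| 0.5 | 1.00 | 0.75 | 25% | 0.187 | 0.162 | 75% | 86% |
| 0.7 | 0.60 | 0.51 | 15% | 0.145 | 0.134 | 93% | 96% |

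**Step 3: against the 2-df group-by-time test of a repeated-measures ANOVA with a group factor.** Noncentral F on 2 and 224 df, with lambda = (57/2) x S / (1 - rho), where S is the sum of squared deviations of the three visit differences from their mean. For differences (0, 0.5, 0), S = 0.1667; at rho 0.5, lambda = 28.5 x 0.1667 / 0.5 = 9.5.

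| Difference at week 24 | rho | 2-df group-by-time | Baseline-adjusted week 12 |
|---|---|---|---|
| none | 0.5 | 78.8% | 86.3% |
| none | 0.7 | 95.2% | 96.0% |
| none | 0.8 | 99.4% | 99.3% |
| half (0.25 SD) | 0.5 | 65.7% | 86.3% |
| half (0.25 SD) | 0.7 | 87.5% | 96.0% |

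The gain runs from about 20 points to nothing, depending on rho and on what remains at week 24. The 2-df test also asks a broader question than a single week-12 contrast, so Step 2 is the like-for-like comparison.

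**The case against.** The strongest reply is that this is a preference, not an error. A change-from-baseline or group-by-time contrast is unbiased under randomisation, and the loss is small when visits are highly correlated. That stands, and it sets the priority.

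Second, the adjusted GEE leaves its covariates unnamed. Baseline may be among them, and group-by-visit may be among the plausible interactions; a SAP that is not shown could say so. It would therefore be wrong to claim that the plan does not use baseline as a covariate; it only does not state it. What the protocol does fix is the three-level ANOVA/Friedman sentence, which a covariate list for the GEE would not alter.

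Third, baseline as a response is not inefficient in itself: a model that constrains the baseline means to be equal across arms recovers the precision. The protocol mentions no such constraint, and ordinary repeated-measures ANOVA does not impose one.

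A reader might also infer a much larger loss: that the treatment effect is averaged with a visit at which no effect can exist, giving (0 + d12 + d24)/3. At rho 0.5 with no week-24 difference, such a test has 19% power against 86% for the adjusted week-12 contrast. The documents do not support that reading. The protocol never names a group main effect averaged over the three visits as its treatment test, and the Friedman alternative cannot carry a group factor. The comparison also changes two things at once: even a baseline-adjusted average of weeks 12 and 24 has only about 46% power in that scenario. Much of the drop therefore comes from averaging in week 24, not from how baseline is handled.

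**Conclusion.** The point holds as a free improvement with the priority of a minor recommendation. The protocol analyses the pre-treatment value as a response level and does not state that it is a covariate. Baseline adjustment would cut the variance of the week-12 difference by 15% to 35% for rho between 0.7 and 0.3. For a 0.5 SD difference with 57 per arm, that is 3 to 18 points of power over a change contrast. Against the 2-df group-by-time test, the gain can fall below one point when rho is high. All of this rests on an assumed rho, effect size and equal-correlation structure.

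There is no bias. Dilution of the effect to (d12 + d24)/3 would arise only if a group main effect averaged over all three visits were adopted as the treatment test, which the protocol does not say.

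**What to change.** Reword the Plan of analysis so that the GEE already planned carries the comparison of the arms:

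- Responses: the week-12 and week-24 values only.
- Terms: randomised group, visit, group-by-visit, and the baseline value of the same outcome as a covariate.
- Report the baseline-adjusted difference between Groups A and B with 95% CI at each visit.
- Adjust only for covariates measured before treatment. The Data Collection section places measurement after randomisation and drug dispensing, so state that the baseline sample precedes the first dose.
- Keep the three-level repeated-measures ANOVA/Friedman analysis as a description of change over time.

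The cost is a rewritten paragraph. No further patients, visits, measurements or software are needed.
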